2.0 Background

Importance of the problem. The significance of this project lies in the fact that it is the first step (adaptation and feasibility testing) in a research continuum that will lead to validation of a technology-based intervention for improving self-management, symptom management, health care utilization and ultimately quality of life among populations of children with complex chronic conditions (CCC) and their caregivers. As such, this project is directly in line with the stated core mission of the NIH's National Institute of Nursing Research.

Sickle cell disease (SCD) is a highly complex and challenging chronic disorder that negatively influences quality of life in children and families of those with the disorder.¹ SCD is a hereditary CCC that almost exclusively affects African Americans. Nationwide, an estimated 72,000 to 98,000 individuals have SCD; >90% of these are African American.² Symptoms of SCD often occur within the first year of life and require lifelong preventive management. SCD is a hemoglobinopathy characterized by an altering in the shape of red blood cells in response to hypoxia, stress, or acidosis.^{3,4} These abnormally shaped cells occlude small vessels and cause inflammation, pain, infarction, and ultimately, organ damage.^{3,4} The physiological sequelae of SCD lead to high health care needs and utilization, and often, to comorbidities and early death.^{5,6} Many children with CCC, particularly SCD, and their families have high health care needs that are frequently unmet or inadequately met. SCD is one of several CCCs affecting children that could benefit from improved self and family management care, such as epilepsy, cerebral palsy, and chronic respiratory disease.^{7,8}

SCD as a CCC based in health disparity. Because children with SCD and their families have high health care and “other” needs that endure throughout their lifetime, preventive actions are necessary in early childhood to avoid or mitigate adverse effects of the disease process. For optimal management and minimal adverse effects, persons with SCD and/or caregivers must coordinate appointments with various providers, continuously monitor symptoms, and obtain preventive home therapies. Often, challenges are pronounced early in the disease process as caregivers learn about the disease and treatments. Typically, a multidisciplinary team is established and caregivers learn to coordinate and maintain care. However, SCD primarily affects an underserved population (i.e., African Americans) who disproportionately face barriers such as transportation, obtaining childcare, and taking time from work. In fact, low-income children with SCD have significantly higher hospitalizations and ED visits than other children in general.⁹

Methods to enhance self-care of SCD by affected individual and the family are needed. Self-care interventions to prevent adverse effects of the disease process have not been well implemented for children with SCD. Fortunately, assistance with providing reliable sources of disease and treatment related information, decision-making, and communication with the care team via technology improve family-centered self-management behaviors in older children (ages 10-17 years) with SCD.¹⁰ Assisting families caring for an infant or young child with SCD via a similar technology-based model may lead to improved self-management and quality of life outcomes. Providing resources via this mechanism may reduce burden and maximize outreach

to this difficult to reach, underserved, high needs population. Traditional barriers to care such as transportation, childcare, and work conflicts can be overcome. Long-term management of SCD and prevention of adverse outcomes also requires support for self-management skill development. Through technological resources and collaborative relationships with providers, caregivers can receive support to develop self-management skills.

Theoretical Framework. The Pediatric Self-Management Framework⁷ guides the present study and provides an ideal underpinning to our proposed methods because it outlines multilevel influences that affect self-management and family-centered self-management behaviors through multiple processes, and guides prediction of the outcomes associated with influences, behaviors, and processes. According to this framework, self-management influences, processes, and behaviors exist on the individual, family, community, and health care system domains. Because this study will focus on children ages birth-7 years and their caregivers, and on the caregiver-provider relationship, we will target the family and health care system domains. Specific influences, processes, and behaviors addressed in this study are outlined in Table 1.

Table 1: Intervention Self-Management Influences, Processes, and Behaviors

Self-management Influences	Self-management Processes	Self-management Behaviors

 • Family disease and treatment knowledge • Parental monitoring and supervision • Parental involvement • Patient (parental)-provider communication 	
 • Determining child's health care needs • Communication with medical team • Seeking disease and treatment related information • Determining child's health care needs • Allocation of treatment responsibility • Learning about patient's disease and treatments • Provision of support for treatment regimens • Modification of communication styles • Shared decision making 	
 • Giving medication and treatments such as home physical and respiratory therapy • Attending clinic appointments • Monitoring and tracking symptoms • Introducing and supporting lifestyle modifications • Providing recommended therapies

3.0 Intervention to be studied

The intervention is a multicomponent (3-part) technology-based package. The intervention targets influences and processes informed by the Pediatric Self-Management framework (Table 1). Component 1 (education) consists of continuous access to directed educational resources on the SCD process, treatment, home management strategies, symptom prevention and management strategies. These materials are easily accessible via a mobile device given to caregivers and will include patient-centered PDF files and links to websites developed and tested by authoritative sources. An example includes the patient education materials provided by NIH NHLBI such as the Sickle Cell Disease Infographic: Monitoring Pain (Figure 1). To address potential literacy barriers, an

Figure 1: Example of Educational Material

application that reads PDF files aloud (e.g. @Voice Aloud Reader) is downloaded onto caregiver devices. Component 2 (symptom monitoring and tracking) consists of a mobile-device based publicly available application for tracking and monitoring pain in SCD that also permits upload of symptom logs and text alerts to a health care provider (Voice Crisis Alert). Component 3 (caregiver-provider communication) is based on Jacob et al. (2013)'s intervention with an mHealth intervention for older children with SCD. This component consists of a technology-based connection with a provider who will: respond to alerts delivered via the mHealth application, monitor pain symptoms delivered via the mHealth application, and respond to messages. A provider at the MUSC Pediatric Sickle Cell Clinic will collaborate with caregivers to coach caregivers on the care of the child and provide support to the caregiver.¹⁰ Caregivers will receive a daily message using a semi-structured protocol to "check in" with participants and promote engagement. All components are integrated into the web-based app. A secure portal is in place for messaging that encrypts all messages and protects confidentiality.

During Phase I of this study, using an iterative design process and guided caregiver, child and clinician feedback, we developed and refined the intervention by conducting user focus groups and pilot testing the app among a target population of end-users. Specific tasks accomplished during this Phase I, included developing and incorporating age specific language into the app, refining the user graphical user interface, developing and integrating the provider communication component to include clinically relevant disease specific symptoms, and build-out of the clinician's patient portal – where individual patient's data can be accessed for summary viewing. Now, in Phase II, we aim to deploy the intervention in a real-world setting.

Children (5-7) with SCD and their caregivers will complete self-report and proxy assessments as described in Table below; data will be recorded in REDCap by the PI or project coordinator

Major tasks and domains	Measures/instruments/questions and Cronbach's alpha ()	Data sources and time points
Demographics/clinical characteristics	Age, child age, health history, race/ethnicity, medications, health care utilization, rural/urban residence, insurance, caregiver demographics, family characteristics	Caregiver interview; baseline
Reach: Sample Recruitment	Monitoring of sample representativeness; types of recruitment activities; rates of recruitment; % eligible, consented, provided with informational session	Recruitment tracking forms; quality checks by PI; weekly meetings with mentor, clinic staff, and research team
Efficacy: Child (by proxy): Pain Fatigue Quality of life Caregiver: Fatigue Emotional distress: anxiety Emotional distress: depressive symptoms	PROMIS Parent Proxy: Pain Interference* ^{21,22} (age 5 and older) PedsQL with Sickle Cell Disease Module (proxy = 0.97) ²³ (age 2 and older) PedsQL Multidimensional Fatigue Scale in Sickle Cell Disease (proxy = 0.95) ²⁴ (age 2 and older) PROMIS Fatigue SF (>0.9) ²⁵	Review and content analysis of transcriptions of text messages; review and content analysis of recorded teleconferences; tracking forms; fidelity checklist; transmissions from web-based application to nurse; post-intervention interviews; weekly

Measures of self-management behaviors: Monitoring and tracking symptoms Attending clinic appointments Administering home medications and treatments	PROMIS Emotional Distress: Anxiety (0.97) ²⁶ PROMIS Emotional Distress: Depressive symptoms SF (0.97) ²⁷ Daily pain severity rating; daily pain type rating # days recorded symptoms; # days and types of recorded treatments; # scheduled clinic appointments attended; # days daily mediation administered; # days PRN medications administered	meeting with mentor, clinic staff, and research team; baseline, mid-intervention, post-intervention, 3-months post-intervention
Adoption: Adherence Acceptability Education Symptom monitoring and tracking Patient-provider communication	# days symptoms recorded; # times educational component accessed; length of time in minutes educational component accessed; # text messages and videoconferences with nurse Caregiver satisfaction; # problems reported; types of problems reported # times accessed educational materials; length of time in minutes educational materials accessed # days recorded symptoms; # contacts (text or videoconferencing) with nurse pertaining to symptoms # and type (screening, referring, coaching, supporting) of contacts (text or videoconferencing) with nurse Collaborate for Parents	Tracking forms; content analysis from text messages and videoconferences with nurse, data transmitted from web-based application; fidelity checklist; weekly meetings with mentor and research team; caregiver interview at end of study
Implementation: Technology Consistency of intervention	# problems encountered with mobile device, # problems reported to research staff; types of problems reported instructional session conducted as planned; fidelity to protocol maintained MAPS	Tracking forms; weekly meeting with mentor and research team; caregiver interview at end of study
Maintenance: Projection of future adoption	# caregivers who would continue intervention; caregiver perception of the intervention; feasibility of nurse role	Caregiver interview at end of study; weekly meetings with mentor, clinic staff, and team

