5.0 Inclusion and Exclusion Criteria/ Study Population

- Eligible caregiver/child dyads will be identified through the staff at the MUSC Pediatric Sickle Cell Clinic. After receiving permission to approach, PI or PC will

screen the potential participants against the inclusion and exclusion criteria. Screening will be documented in REDCap.

Inclusion Criteria

- Children ages 0 – 7 years and parent or primary caregiver 18 years of age or older
- Child with sickle cell disease, as reported by clinician at the MUSC Pediatric Sickle Cell Clinic

Exclusion Criteria

- Parent/caregiver with cognitive disability or delay that precludes ability to participate
- Lack of access to Wi-Fi

Inclusion of Women and Minorities

Both women and minorities will be included in the proposed study. Women are more often than men reported to be the primary caregiver of children with chronic conditions and approximately 66% of caregivers of adults with chronic illness are women. Therefore, it is anticipated that more women will be recruited as participants than men. In addition, SCD occurs almost exclusively in African Americans; therefore, it is anticipated that all or nearly all of the caregiver participants will be African American.

Inclusion of Children

Children ages 0-7 years will be included as part of the child/caregiver dyad. Proxy data will be collected on children younger than 5 years, and older children (ages 5-7 years) without developmental delay will be invited to complete surveys and participate in key informant interviews with the caregiver.

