6.0 Number of Subjects

- N=60 – 30 caregivers of 30 children (0-7 years) with SCD will be recruited.

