12.0 Data Management

Sample size considerations

The purpose of this study is to establish feasibility of implementing the integrated intervention obtain estimates of variability for the primary outcome measures and obtain preliminary indicators of effectiveness of the intervention rather than to confirm or refute hypotheses.

Therefore, sample size considerations focus on precision of estimates. For this feasibility study, we project that we will be able to recruit 30 child/caregiver dyads. With such a sample we will be able to estimate outcome proportions for feasibility measures including recruitment and drop-out with precision ± 0.11 to ± 0.16 for values of the true proportion ranging from 0.10 to 0.30 (or correspondingly, from 0.70 to 0.90). Assuming a drop-out rate of up to 30%, 95% confidence limits can be estimated for impact measures, such as change from pre-to-post in quality of life for child and caregiver with a precision ranging from ± 0.43 to ± 1.35 corresponding to estimated standard deviations for change in quality of life scores ranging from 0.5 to 5.0 SD units.

Demographic and clinical variables obtained at baseline will be described via measures of central tendency (mean, median), variability and frequency distributions as appropriate. Additionally, demographic and clinical characteristics for those who adhered to the study protocol (study completers) versus those who did not adhere (non-adherers and drop-outs) will be compared to better describe the population for this study. For continuous quality of life measures for the child and caregiver the difference between pre and post intervention measurements will be estimated via 95% confidence intervals. To assess preliminary intervention effects, we will conduct repeated measures ANCOVA with symptom (pain) severity and type obtained daily as dependent variable in individual models adjusting for “dose” defined as number of times education module was accessed and total time spent in education modules.

Post-intervention qualitative analyses (Aim 2): Data collected from post-intervention key informant interviews will be analyzed using directed content analysis¹⁹ and nVivo qualitative data analysis software version 11.²⁰ Consistent with the directed content analysis approach, initial coding categories are identified according to the guiding theoretical model, and for this study, will reflect the RE-AIM domains.

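### 0–7 years protocol, Section 12.0: the precision for child quality-of-life change allows only for drop-out, although the child scales start at age 2 or 5, and the printed range does not follow from its stated SDs

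*Combined protocol and SAP*

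**What the plan says.** All references are to the 0–7 years protocol within the Combined protocol and SAP unless stated.

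- **Eligibility (5.0, 6.0).** "Children ages 0 – 7 years and parent or primary caregiver 18 years of age or older"; "30 caregivers of 30 children (0-7 years) with SCD will be recruited". No quota or minimum number by age is set.
- **Child measures (3.0, measures table, Efficacy).** Quality of life: "PedsQL with Sickle Cell Disease Module (proxy = 0.97) ²³ (age 2 and older". Fatigue: "PedsQL Multidimensional Fatigue Scale in Sickle Cell Disease (proxy = 0.95) ²⁴ (age 2 and older". The same cell marks PROMIS Parent Proxy Pain Interference as for age 5 and older. No substitute is named below these ages.
- **Caregiver measures (same table).** "Fatigue Emotional distress: anxiety Emotional distress: depressive symptoms". No caregiver quality-of-life scale is listed.
- **Precision (12.0).** The allowance for losses reads "Assuming a drop-out rate of up to 30%, 95% confidence limits can be estimated for impact measures". The precision itself is given for "change from pre-to-post in quality of life for child and caregiver with a precision ranging from ± 0.43 to ± 1.35". The plan then ties that range to a spread of SDs, with the words "corresponding to estimated standard deviations for change in quality of life scores ranging from 0.5 to 5.0 SD units". Drop-out is the only loss mentioned. Section 12.0 of the 8–17 years protocol carries the same figures, and no child there is under 2.
- **Who gives proxy data.** Section 5.0 (Inclusion of Children) plans proxy data for children under 5. Section 3.0 and the Measures paragraph of Section 10.0 describe self-report and proxy assessments for children aged 5–7 and their caregivers.

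**The concern.** Section 12.0 rests the sample size on precision, not on a test. A child below an instrument's age floor at baseline has no baseline score and so cannot give a pre-to-post difference, even if the child reaches the floor during follow-up. The number of pairs behind the child precision is therefore the number old enough at baseline and still in the study, not simply the number still in the study. One range for child and caregiver together hides that the two counts can differ.

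At stake is how well the study can supply the variability estimates and early indications of effect that Section 12.0 promises for child quality of life, fatigue and pain interference. Correcting the count alone would not be enough, because the printed range does not follow from the SDs that it is said to correspond to.

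**Working it through.** **Inputs.** 30 dyads, drop-out up to 30%, 95% limits, SD of change 0.5 to 5.0, printed range ± 0.43 to ± 1.35 (all Section 12.0); age floors 2 and 5 (Section 3.0); ages 0–7 (Section 5.0). The age mix is not given and is an assumption below.

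**1. The plan's own figure.** Pairs after drop-out: 30 × 0.70 = 21 (not printed). With SDs as labelled, the paired half-width at 21 pairs is:
- z: 1.96 × 0.5/√21 = 0.214 and 1.96 × 5.0/√21 = 2.138
- t, 20 df: 0.228 and 2.276

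Neither end is reproduced. No single number of pairs can do so: 5.0/0.5 = 10, but 1.35/0.43 = 3.14. The lower end would need (1.96 × 0.5/0.43)² = 5.2 pairs and the upper (1.96 × 5.0/1.35)² = 52.7.

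Of the variants tried (z or t, 21 or 30, one or two samples, SD or variance), only one returns both ends: 1.96 × √(2V/21), with V = 0.5 giving 0.428 and V = 5.0 giving 1.353. That treats 0.5 and 5.0 as variances in a two-independent-sample formula, which does not suit a single-group paired change. It also supports 21 as the count used.

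The feasibility proportions do reproduce, at n = 30: 1.96 × √(0.1 × 0.9/30) = 0.107 and 1.96 × √(0.3 × 0.7/30) = 0.164.

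**2. Expected child pairs.** With k children under 2 at baseline and drop-out unrelated to age, PedsQL pairs = 0.70 × (30 − k):
- k = 0: 21
- k = 1: 20.3
- k = 3: 18.9
- ages even over 0–7 (2 of 8 single-year ages, k = 7.5): 15.75, so 15 to 16

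Pain Interference on the same even-age assumption (3 of 8 single-year ages): 0.70 × 11.25 = 7.9, about 8.

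**3. Effect on the interval.** Widening is relative to 21 pairs; half-width is t × SD/√n with SDs as labelled.

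| Pairs | Widening, z | Widening, t | SD 0.5 | SD 5.0 |
|---|---|---|---|---|
| 21 | 1.000 | 1.000 | ± 0.23 | ± 2.28 |
| 20 | 1.025 | 1.028 | ± 0.23 | ± 2.34 |
| 19 | 1.051 | 1.059 | ± 0.24 | ± 2.41 |
| 16 | 1.146 | 1.171 | ± 0.27 | ± 2.66 |
| 15 | 1.183 | 1.217 | ± 0.28 | ± 2.77 |
| 8 | 1.620 | 1.837 | ± 0.42 | ± 4.18 |

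**4. Drop-out that would keep 21 PedsQL pairs.** 1 − 21/(30 − k) is 27.6% at k = 1, 22.2% at k = 3 and 6.7% at k = 7.5. In whole percentages that is no more than 27%, 22% and 6%. Check: 29 × 0.73 = 21.2; 27 × 0.78 = 21.1; 22.5 × 0.94 = 21.2.

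**5. If 0.5 and 5.0 are variances of change.** The paired t half-width, t × √(V/n), is ± 0.32 to ± 1.02 at 21 pairs, ± 0.39 to ± 1.24 at 15 (2.145 × √(0.5/15) and 2.145 × √(5.0/15)), and ± 0.59 to ± 1.87 at 8 (2.365 × √(0.5/8) and 2.365 × √(5.0/8)).

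**The case against.** The strongest reply is that little depends on this figure. Section 12.0 says the study is not meant to confirm or refute hypotheses, and no test, threshold or progression rule uses the precision. The age floors stand beside the instruments and eligibility from birth is explicit, so a careful reader can see the problem; only the arithmetic is missing. The 30% is an upper limit, and lower drop-out can offset the loss. All of this stands, and it is why the point is minor.

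The loss is also only an expectation. Nine of 30 dyads are allowed for as drop-outs, and a child under 2 who is one of them costs no further pair. A reader might infer that every child under 2 removes a pair, or that the count must fall below 21. The documents support neither: they give no age mix, and there is no loss if no child under 2 enrols. The protocol's background speaks of infants, but that sets no number.

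A reader might also infer that the printed range is too narrow throughout. On the SD label its lower end is wider than the paired formula gives (± 0.43 against ± 0.23 at 21 pairs), and its upper end is narrower (± 1.35 against ± 2.28). If variances were meant, the printed range would still cover 15 pairs (± 0.39 to ± 1.24), though not 8. What stands is that the figure rests on a count and a formula that do not fit the child outcomes.

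Finally, a reader might infer that 30 dyads are too few. Keeping 21 PedsQL pairs at even ages and 30% drop-out would take 21/(0.70 × 0.75) = 40 dyads, but the plan sets no precision target that would require this.

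**Conclusion.** The point holds, as a minor one confined to the secondary aim. Section 12.0 states a single precision for child and caregiver that allows for drop-out but not for the age floors of the child instruments. If drop-out is unrelated to age, the PedsQL interval is unchanged with no child under 2, about 3% wider with one, 5–6% wider with three, and 15–22% wider with ages even over 0–7. Pain Interference is affected more, with about 8 pairs at even ages. Those last two figures rest on an assumed age mix.

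The counts also assume that proxy data are collected below age 5, as Section 5.0 says. Read literally, Sections 3.0 and 10.0 would make 5 the working floor for the PedsQL measures too, so the conflict bears on the numbers.

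The mismatch between the printed range and its SD label is a separate error and does not depend on the age mix. That variances in a two-sample formula were used is an inference from the arithmetic, not something the plan states. The primary feasibility aim, the caregiver measures and the daily pain ratings are not affected by the age floors.

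**What to change.** 1. In Section 12.0 of the 0–7 years protocol, state the expected number of pairs for each child instrument (age 2 and over for the PedsQL measures, age 5 and over for Pain Interference) under a stated age mix and drop-out, and give the precision on that number. Keep 21 pairs for the caregiver measures and name them: fatigue, anxiety and depressive symptoms.
2. Recompute with the paired one-sample formula, t × SD/√n. If 0.5 to 5.0 are SDs of change, this gives ± 0.23 to ± 2.28 at 21 pairs, ± 0.28 to ± 2.77 at 15 and ± 0.42 to ± 4.18 at 8. If they were meant as variances, say so and recompute on that basis. Make the same SD correction in Section 12.0 of the 8–17 years protocol.
3. Reconcile Sections 3.0 and 10.0 (Measures) with Section 5.0 (Inclusion of Children) on whether proxy data are collected for children under 5, before fixing the pair counts.

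The cost is wording and figures only; the number of dyads, recruitment and visits do not change. The downside is a less favourable stated precision for the child outcomes than for the caregiver measures and, if the SD label is right, a wider upper end for all of them.
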